**Table 6-4      Clinically relevant drug interactions: inducers and inhibitors of isoenzyme CYP3A**

---

**Inducers**

---

**Strong inducers:**

avasimibe, carbamazepine, enzalutamide, mitotane, phenobarbital, phenytoin, rifabutin, rifampin (rifampicin), St. John's wort (*Hypericum perforatum*)

**Moderate inducers:**

bosentan, efavirenz, etravirine, genistein, lersivirine, lopinavir, modafinil, nafcillin, ritonavir, semagacestat, talviraline, thioridazine, tipranavir

**Weak inducers:**

amprenavir, aprepitant, armodafinil (R-modafinil), bexarotene, boceprevir, brivacetam, clobazam, danshen, dexamethasone, Echinacea, eslicarbazepine, garlic (*Allium sativum*), gingko (*Ginkgo biloba*), ginseng, glycyrrhizin, methylprednisolone, nevirapine, oxcarbazepine, pioglitazone, prednisone, pleconaril, primidone, quercetin, raltegravir, ritonavir, rufinamide, sorafenib, Stribild (combo of elvitegravir, cobicistat, emtricitabine, and tenofovir), sulfipyrazone, telaprevir, terbinafine, ticagleror, ticlopidine, topiramate, troglitazone, vemurafenib, vicriviroc/ritonavir, vinblastine

---

**Inhibitors**

---

**Strong inhibitors:**

boceprevir, clarithromycin, cobicistat, conivaptan, danoprevir/ritonavir, eltegravir/ritonavir, grapefruit juice, indinavir, indinavir/ritonavir, itraconazole, ketoconazole, lopinavir/ritonavir, mibefradil, nefazodone, nefinavir, posaconazole, ritonavir, saquinavir, saquinavir/ritonavir, telaprevir, telithromycin, tipranavir/ritonavir, troleandomycin, voriconazole

**Moderate inhibitors:**

Amprenavir, aprepitant, atazanavir, atazanavir/ritonavir, casopitant, cimetidine, ciprofloxacin, crizotinib, cyclosporine, darunavir, darunavir/ritonavir, diltiazem, dronedarone, erythromycin, fluconazole, fosamprenavir, grapefruit juice (*Citrus paradisi* fruit juice), imatinib, lomitapide, netupitant, nilotinib, *Schisandra sphenanthera*, tofisopam, verapamil

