#### **6.1.3.1 Cytochrome P450 and P-glycoprotein (PgP) inhibitors/inducers/substrates**

Everolimus is metabolized by CYP3A4 in the liver and to some extent in the intestinal wall.

Therefore, the following are recommended:

- Co-administration with strong inhibitors of CYP3A4 (e.g., ketoconazole, itraconazole, ritonavir) or P-glycoprotein (PgP) should be avoided and may cause increased everolimus concentrations.
- Co-administration with moderate CYP3A4 inhibitors (e.g., erythromycin, fluconazole) or PgP inhibitors should be used with caution. If a patient requires co-administration of moderate CYP3A4 inhibitors or PgP inhibitors, reduce the dose of everolimus to half the currently used dose (see [Table 6-9](#) for everolimus dose modifications). Additional dose reductions may be required to manage toxicities. If the inhibitor is discontinued, consider a washout period of at least 2-3 days (average for the most commonly used moderate

[figure not shown]
inhibitors), before the study drug is returned to the dose used prior to initiation of the moderate CYP3A4/PgP inhibitor.

- Co-administration with strong inducers of CYP3A4 should be avoided.
- If a patient requires co-administration of strong CYP3A4 inducers (i.e., phenytoin, carbamazepine, rifampin, rifabutin, phenobarbital, St. John's wort), an increase in the dose of everolimus up to twice the currently used daily dose should be considered, using 5mg increments or less (see [Table 6-9](#) for everolimus dose modifications). This dose adjustment of everolimus is predicted to achieve similar AUC to the range observed without inducers. However, there are no clinical data with this dose adjustment in patients receiving strong CYP3A4 inducers. If the strong inducer is discontinued, consider a washout period of at least 3-5 days (reasonable time for significant enzyme de-induction), before the study drug dose is returned to the dose used prior to initiation of the strong CYP3A4/PgP inducer.

It is to be noted that:

- Local radiotherapy for analgesic purposes or for lytic lesions at risk of fracture may be carried out if required. Whenever possible, these patients should have a tumor assessment of the lesion(s) before they actually receive the radiotherapy. No dose modification of study treatment is needed during radiotherapy.
- Everolimus may affect the response to vaccinations making it less effective. Live vaccines should be avoided while a patient is treated with everolimus.

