- Lipid-lowering drugs may be given in case of hyperlipidemia.

Otherwise, the use of other concomitant medication/therapy deemed necessary for the care of the patient is allowed. The investigator should instruct the patient to notify the study site about any new medications she takes after the start of the study drug. All medications (other than study drug) and significant non-drug therapies (including physical therapy and blood transfusions) administered after the patient starts study treatment and for up to 28 days after study drug discontinuation must be listed on the Concomitant medications/Significant Nondrug Therapy After Start of Study Drug eCRF. The first regimen of antineoplastic medication/treatments received after study treatment discontinuation must also be recorded in the antineoplastic treatment eCRF.

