**Weak inhibitors:**

almorexant, alprazolam, alprazolam, amiodarone, amlodipine, amlodipine, atorvastatin, azithromycin, berberine, bicalutamide, bicalutamide, blueberry juice, cilostazol, cilostazol, cimetidine, clotrimazole, clozoxazole, cranberry juice, cyclosporine, delavirdine, everolimus, fluoxetine, fluvoxamine, fosaprepitant, ginkgo, goldenseal, isoniazid, isoniazid, ivacaftor, lacipidine, linagliptin, nilotinib, oral contraceptives, pazopanib, peppermint oil, propiverine, ranitidine, ranitidine, ranolaxine, ranolazine, resveratrol, roxithromycin, Seville orange, simeprevir, sitaxentan, tabimorelin, tacrolimus, teriflunomide, ticagrelor, tipranavir/ritonavir, tolvaptan, zileuton

---

**Table 6-5      Clinically relevant drug interactions: substrates, inducers, inhibitors of PgP and PgP/CYP3A dual inhibitors**

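### Table 6-4 lists five agents in two CYP3A4 inhibitor classes, leaving the everolimus dose ambiguous for cimetidine, and Section 6.2.2.1 conflicts in wording with Section 6.1.3.1 on fluconazole

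*Protocol*

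**What the plan says.** Section 6.1.3.1 makes the action depend on the class of the interacting drug.

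- Strong: "Co-administration with strong inhibitors of CYP3A4 (e.g., ketoconazole, itraconazole, ritonavir) or P-glycoprotein (PgP) should be avoided".
- Moderate: "Co-administration with moderate CYP3A4 inhibitors (e.g., erythromycin, fluconazole) or PgP inhibitors should be used with caution". If the drug is required, the instruction is to "reduce the dose of everolimus to half the currently used dose", with a pointer to Table 6-9.
- Weak: no CYP3A4 rule. These drugs fall under the closing permission that "the use of other concomitant medication/therapy deemed necessary for the care of the patient is allowed".

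Table 6-4 is where the investigator finds the class. Its strong list contains "danoprevir/ritonavir, eltegravir/ritonavir, grapefruit juice, indinavir" and its moderate list contains "erythromycin, fluconazole, fosamprenavir, grapefruit juice", so grapefruit juice is in both. Its moderate list also contains "casopitant, cimetidine, ciprofloxacin, crizotinib, cyclosporine" and its weak list "cilostazol, cilostazol, cimetidine, clotrimazole, clozoxazole, cranberry juice, cyclosporine", so cimetidine and cyclosporine are in both. Nilotinib is likewise moderate and weak, and tipranavir/ritonavir is strong and weak. No footnote separates the entries by dose, formulation or juice strength.

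Fluconazole is in one inhibitor list only, the moderate one, and Section 6.1.3.1 names it as a moderate example. Item 4 of the stomatitis guidance in Section 6.2.2.1 groups it with ketoconazole and itraconazole, says that these should be avoided systemically in every patient, and describes their effect on everolimus metabolism as strong inhibition.

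**The concern.** Where class determines dose, an agent in two classes has two instructions. Section 6.1.3 requires patients to consult the investigator before taking any other product, and Section 6.2.2.10 sends the investigator back to Section 6.1.3 for dose changes due to concomitant medication. That safeguard works only if the reference table gives one answer. At stake is overexposure if a needed reduction is missed, or underdosing if an unneeded one is made.

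The fluconazole wording matters because Section 2.2.1 puts stomatitis at about 44-64% of everolimus-treated patients, so a decision about an antifungal is foreseeable. A site reading only Section 6.2.2.1 finds no dose instruction for a patient who does need the systemic drug; Section 6.1.3.1 has one.

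**Working it through.** There is no plan figure to reproduce. The check is a cross-match of the Table 6-4 inhibitor lists, followed by the dose that each listing implies.

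**Step 1. Agents in more than one inhibitor class**

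| Overlap | Agents | Count |
|---|---|---|
| Strong and moderate | grapefruit juice | 1 |
| Moderate and weak | cimetidine, cyclosporine, nilotinib | 3 |
| Strong and weak | tipranavir/ritonavir | 1 |

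Total: 1 + 3 + 1 = 5.

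**Step 2. Which overlaps can affect a patient**

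- Cyclosporine: exclusion criterion 9 bars chronic systemic immunosuppression.
- Nilotinib: Section 6.1.3 prohibits other anticancer agents.
- Tipranavir/ritonavir: an HIV treatment, and exclusion criterion 11 bars known HIV seropositivity.
- Grapefruit juice: the half-dose rule applies only when co-administration is required. That is hardly ever so for a juice, so both listings lead to avoidance.
- Cimetidine: nothing else in the protocol bars it. It is not among the PgP or dual inhibitors in Table 6-5, so the PgP half-dose rule does not settle its dose either.

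**Step 3. Cimetidine, if required, under each listing**

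The moderate rule is new dose = current dose / 2. The weak listing leaves the dose unchanged. Table 6-9 sets the floor at 5 mg every other day, which averages 5/2 = 2.5 mg/day.

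| Current everolimus | If moderate | If weak |
|---|---|---|
| 10 mg daily | 10/2 = 5 mg daily | 10 mg daily |
| 5 mg daily | 5/2 = 2.5 mg/day, i.e. 5 mg every other day | 5 mg daily |
| 5 mg every other day | 2.5/2 = 1.25 mg/day, below the floor, so discontinue | 5 mg every other day |

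The listings differ two-fold at the first two levels. At the lowest they differ between stopping and continuing.

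**Step 4. Fluconazole, the sections side by side**

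| Place | Description | Action |
|---|---|---|
| Section 6.1.3.1 | named moderate example | caution; half dose if required |
| Table 6-4 | moderate only | as above |
| Section 6.2.2.1, item 4 | strong inhibition | avoid systemically in every patient; no dose given if required |

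The conflict lies in the stated reason and in the breadth of the instruction, and it is between sections.

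**The case against.** The strongest case for leaving this alone is that little remains after the exclusions. One drug is clearly affected, prior consultation is required, and enrollment is closed: the Amendment 5 rationale gives 64 + 19 = 83 patients on treatment at the June 2016 cut-off, out of 202 enrolled. That stands as a limit on size. It does not make the point clerical, because the table still gives two doses for the same patient.

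The fluconazole passages can also be read together: avoid the systemic drug in mouth care, and halve everolimus if it is truly needed. That largely stands. A reader might infer that Section 6.2.2.1 reclassifies fluconazole as a strong inhibitor. It does not; it assigns no class, and sits in a list whose aim is to withhold antifungals unless infection is diagnosed and then to prefer topical ones. What remains is that the instruction covers every patient and gives a reason at odds with the class used elsewhere.

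Three further readings are tempting and unsupported.

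- That the documents show which of the two listings is wrong. The reference note under Table 6-5 attributes the data to an internal interaction memo that summarizes three sources, and the memo is not included. Repeated names within the weak list suggest merged lists, but that is an inference.
- That rifampin and St John's wort, which Table 6-5 also lists as dual inhibitors, have no clear dose direction. Section 6.1.3.1 and Table 6-4 name both as strong inducers, which largely settles it.
- That a missed reduction in the Extension Phase would leave no trace because concomitant medications are not collected then (Section 10.3.2). Section 9.2 still requires source notes, and Section 7.1.4 still collects dispensing and adverse event data. What is lost is the routine database entry.

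**Conclusion.** The point holds as a minor, low-frequency dosing-safety correction. Five agents are double-listed in Table 6-4, and one of them, cimetidine, leaves a practical conflict: 5 mg versus 10 mg from a 10 mg daily dose, and discontinuation versus no change at 5 mg every other day. The fluconazole item is a conflict of wording and rationale between Section 6.2.2.1 and Section 6.1.3.1 with Table 6-4.

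This rests on three assumptions: that grapefruit juice is hardly ever required, that the exclusions in Step 2 largely keep the other three agents out, and that the memo cited under Table 6-5 also underlies Table 6-4. The number of patients taking cimetidine or systemic fluconazole is not given and is probably small. A reader might infer that the primary result is at risk; nothing here changes the sample size or the PFS analysis.

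**What to change.** 1. In Table 6-4, list each of the five agents once, in the class that the cited interaction memo supports. List grapefruit juice as strong, that is, avoid.
2. Until that is done, add an interim sentence: an agent that appears in two inhibitor classes of Table 6-4 follows the stricter one. Limiting it to those inhibitor lists leaves the strong-inducer rule and the PgP half-dose rule untouched.
3. Reword item 4 of Section 6.2.2.1 so that systemic fluconazole is avoided where possible and, if required, follows the moderate-inhibitor half-dose rule in Section 6.1.3.1.

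The drafting cost is one table, one reworded sentence and one added sentence, with a clinical pharmacology check and the approvals that Section 12.1 requires for any amendment. Sample size, data collection and analysis do not change. The interim rule has a clinical cost that should be stated with it: if the weaker class proves right for cimetidine, everolimus would have been halved without need or, at 5 mg every other day, stopped without need. That is why the stricter class should only bridge the time until the memo is checked.

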**Weak inhibitors:**

almorexant, alprazolam, alprazolam, amiodarone, amlodipine, amlodipine, atorvastatin, azithromycin, berberine, bicalutamide, bicalutamide, blueberry juice, cilostazol, cilostazol, cimetidine, clotrimazole, clozoxazole, cranberry juice, cyclosporine, delavirdine, everolimus, fluoxetine, fluvoxamine, fosaprepitant, ginkgo, goldenseal, isoniazid, isoniazid, ivacaftor, lacipidine, linagliptin, nilotinib, oral contraceptives, pazopanib, peppermint oil, propiverine, ranitidine, ranitidine, ranolaxine, ranolazine, resveratrol, roxithromycin, Seville orange, simeprevir, sitaxentan, tabimorelin, tacrolimus, teriflunomide, ticagrelor, tipranavir/ritonavir, tolvaptan, zileuton

---

**Table 6-5      Clinically relevant drug interactions: substrates, inducers, inhibitors of PgP and PgP/CYP3A dual inhibitors**

**Substrates**

afatinib, alfuzosin, aliskiren, alogliptin, ambrisentan, apixaban, apremilast, aprepitant, atorvastatin acid, atorvastatin, azithromycin, boceprevir, bosentan, carvedilol, caspofungin, ceritinib, cerivastatin, citalopram, colchicine, CP-481,715, cyclosporine, dabigatran, digoxin, docetaxel, domperidone, doxepin, doxorubicin, eribulin, everolimus, fentanyl, fexofenadine, fidaxomicin, fluvastatin, fosamprenavir, gatifloxacin, idelalisib, iloperidone, indacaterol, indinavir, irbesartan, lacosamide, lapatinib, levetiracetam, levofoxacin, linagliptin, linezolid, loperamide, losartan, maraviroc, mirabegron, moxifloxacin, naloxegol, nateglinide, nevirapine, nintedanib, Iodaterol, paclitaxel, pantoprazole, paroxetine, pazopanib, phenytoin, posaconazole, pravastatin, proguanil, quinidine, quinine, ranolazine, riociguat, risperidone, ritonavir, rivaroxaban, saquinavir, silodosin, simeprevir, simvastatin, sirolimus, sitagliptin, sofosbuvir, sorafenib, tacrolimus, telaprevir, tenofovir, ticagrelor, tipranavir, tolvaptan, topotecan, umeclidinium, valsartan, vardenafil, vincristine, voclosporin, voriconazole

**Inducers**

avasimibe, carbamazepine, efavirenz, genistein, phenytoin, quercetin, rifampin, St John's wort

**PgP Inhibitors and PgP/CYP3A Dual Inhibitors**

PgP Inhibitors

alogliptin, canagliflozin, cremophor RH40, curcumin, ketoconazole, lapatinib, lopinavir/ritonavir, mirabegron, propafenone, simeprevir, valspar, vandetanib, voclosporin

PgP/CYP3A Dual Inhibitors

amiodarone, azithromycin, captoril, carvedilol, clarithromycin, conivaptan, diltiazem, dronedarone, elacridar, erythromycin, felodipine, fluvoxamine, ginkgo (*Ginkgo biloba*), indinavir, indinavir/ritonavir, itraconazole, mibepradil, milk thistle (*Silybum marianum*), neflifavir, nifedipine, nitrendipine, paroxetine, quercetin, quinidine, ranolazine, rifampin, ritonavir, saquinavir/ritonavir, *Schisandra chinensis*, St John's wort (*Hypericum perforatum*), talinolol, telaprevir, telmisartan, ticagrelor, tipranavir/ritonavir, tolvaptan, verapamil

Reference: Internal Clinical Pharmacology Drug-drug interaction (DDI) memo, updated April-2015 which summarizes DDI data from three sources including the FDA's "Guidance for Industry, Drug Interaction Studies", the University of Washington's Drug Interaction Database, and Indiana University School of Medicine's Drug Interaction Table.

## 6.2 Dose modifications and known undesirable effects of study drug/treatment

### 6.2.1 Everolimus

As of 31 March 2016 approximately 35,801 patients with various malignancies (excluding patients who received marketed Afinitor®/ Votubia®) have been treated with everolimus in either Novartis-sponsored clinical studies, individual patient supply programs or investigator sponsored clinical studies.

The most common adverse reactions (incidence  $\geq 10\%$  in at least one pivotal trial) were (by decreasing order) stomatitis, rash, fatigue, diarrhea, infections, nausea, decreased appetite, anemia, dysgeusia, pneumonitis, edema peripheral, hyperglycemia, asthenia, pruritus, weight decrease, hypercholesterolemia, epistaxis, cough, and headache. The most common grade 3-4 adverse reactions (incidence  $\geq 2\%$  in at least one pivotal trial), were stomatitis, anemia, hyperglycemia, fatigue, infections, pneumonitis, diarrhea, asthenia, thrombocytopenia, neutropenia, dyspnea, lymphopenia, proteinuria, hemorrhage, hypophosphatemia, rash,

hypertension, aspartate aminotransferase (AST) increased, alanine aminotransferase (ALT) increased, pneumonia and diabetes mellitus. For more details about clinically notable adverse events, refer to the most recent everolimus investigator brochure. Management of specific toxicities is described in [Section 6.2.2](#).

### **6.2.1.1 Letrozole**

The most frequently reported adverse reactions (>20%) were hot flashes, arthralgia, flushing, asthenia, edema, arthralgia, headache, dizziness, hypercholesterolemia, sweating increased, bone pain and musculoskeletal pain. Use of letrozole can also cause decreases in bone mineral density. Increases in total cholesterol may occur. Letrozole may be taken with or without food. Refer to the package insert of the local supply of letrozole for management of toxicities and dose adjustments.

### **6.2.1.2 Exemestane**

The most frequently reported adverse effects for exemestane are gastrointestinal disturbances, hot flushes, arthralgia, myalgia, sweating, fatigue, and dizziness. Other reported effects include headache, insomnia, somnolence, depression, skin rashes, alopecia, asthenia, and peripheral and leg edema. Thrombocytopenia and leucopenia have been reported occasionally. Reductions in bone mineral density can occur with long-term use of exemestane. A total of 1058 patients were treated with exemestane 25 mg once daily in the clinical trials program. Exemestane was generally well tolerated, and adverse events were usually mild to moderate. Adverse events occurring in greater than 10% of patients include hot flushes (14%), nausea (11.9%), insomnia, headache, increased sweating, joint and musculoskeletal pain, and fatigue (USPI; Aromasin SmPC August 2008 (UK as RMS for EU MRP)). Androgenic effects were reported in a limited number of patients (4.3%) ([Buzdar 2003](#)). Refer to the package insert of the local supply of exemestane for management of toxicities and dose adjustments.

## **6.2.2 Management of specific everolimus-related toxicities**

Permitted everolimus (RAD001) dose adjustments are described in [Table 6-7](#), [Table 6-8](#), [Table 6-9](#), [Table 6-10](#), and [Table 6-11](#).

### **6.2.2.1 Management of stomatitis/oral mucositis/mouth ulcers**

Patients with a clinical history of stomatitis/mucositis/mouth ulcers and those with gastrointestinal morbidity associated with mouth/dental infections, irritation of esophageal mucosa e.g. gastroesophageal reflux disease (GERD) and pre-existing stomatitis/mucositis must be monitored even more closely. Patients should be instructed to report the first onset of buccal mucosa irritation/reddening to their study physician immediately.

Stomatitis/oral mucositis/mouth ulcers due to study drug should be treated using local supportive care. Please note that investigators in earlier trials have described the oral toxicities associated with everolimus as mouth ulcers, rather than mucositis or stomatitis. If examination reveals mouth ulcers rather than a more general inflammation of the mouth, please classify the adverse event as such. As noted in [Section 6.1](#), patients in countries where the alcohol-free 0.5mg/5ml dexamethasone oral solution is commercially available, randomized to dexamethasone will be prescribed a 0.5mg/5ml dexamethasone mouth rinse to swish and

expectorate 3 times per day. Treatment of stomatitis/oral mucositis/mouth ulcers for patients randomized to standard of care may include the following measures in conjunction with institutional standards:

1. For mild toxicity (grade 1), use conservative measures such as non-alcoholic mouth wash or salt water (0.9%) mouth wash several times a day until resolution.
2. For more severe toxicity (grade 2 in which case patients have pain but are able to maintain adequate oral alimentation, or grade 3 in which case patients cannot maintain adequate oral alimentation), the suggested treatments are topical analgesic mouth treatments (i.e., local anesthetics such as benzocaine, butyl aminobenzoate, tetracaine hydrochloride, menthol, or phenol) with or without topical corticosteroids, such as triamcinolone oral paste 0.1% (Kenalog in Orabase®).
3. Agents containing alcohol, hydrogen peroxide, iodine, and thyme derivatives may tend to worsen mouth ulcers. It is preferable to avoid these agents.
4. Antifungal agents must be avoided unless a fungal infection is diagnosed. In particular, systemic imidazole antifungal agents (ketoconazole, fluconazole, itraconazole, etc.) should be avoided in all patients due to their strong inhibition of everolimus metabolism, therefore leading to higher everolimus exposures. Therefore, topical antifungal agents are preferred if an infection is diagnosed. Similarly, antiviral agents such as acyclovir should be avoided unless a viral infection is diagnosed.

Additional measures for management of stomatitis consistent with institutional standards should be utilized for patients randomized to standard of care.

